## **4. STUDY DESIGN**

*Overview of Research Design.* We will conduct a cluster randomized controlled clinical trial to evaluate the efficacy of the CPOP intervention within the CP prenatal care group environment. The intervention will take place during the prenatal period and participants

will be assessed pre-intervention and post-intervention while still pregnant and followed through the first year postpartum to evaluate infant and maternal outcomes.

***Intervention Setting.*** The study will take place at 5 healthcare facilities that offer CP in the San Francisco Bay Area, most of which are community-based. The initiation of study activities in sites will be staggered in three waves approximately nine months apart, with two sites starting in each wave. CP groups at these 5 sites are conducted in either English or Spanish. We will recruit a minimum of 2-5 CP facilitators at each site to serve as either intervention or control facilitators. Facilitators will be randomized to one of two groups: 1) Intervention or 2) Control. Intervention facilitators will be trained in the intervention, which will include the facilitators practicing the Intervention delivery in a group of non-study CP moms. When study groups are initiated, the facilitators will conduct the interventions in approximately 3-4 cycles of prenatal groups. In each cycle, intervention facilitator will integrate the 2 intervention modules into 2 of their 10 CP group sessions. Control facilitators will not be trained and will not present the intervention modules within their CP groups. The control groups will receive the usual care CP curriculum. CP groups consist of 8-12 pregnant women of a similar gestational phase.

***CP Facilitators.*** We have identified a Site Champion at each CP site, an individual with influence and connection to the clinical and administrative leadership at the health care facility. Study staff will work with these Site Champions to present an overview of the study to the facilitators and to ask them to enroll in the study. They will be assured that they are free to participate or not, however, they will be aware that their site had made a group decision to participate. The facilitators will be randomized into the Intervention or the Control arm of the study. This means that all of the pregnant women enrolled in a particular facilitator's assigned CPOP study groups will either be Intervention or Control participants.

***CPOP Study Participants.*** Pregnant women enrolled in the CP prenatal care groups identified as study groups at each site will be invited to participate in the study. We expect that most but not all women will agree to participate in the study. However, within the Intervention CP groups, all of the women will receive the OH-integrated intervention modules (unless unenrolled women choose not to), but only enrolled study participants will complete the study questionnaire assessments and dental exams, and the salivary bacterial assays and questionnaires at 12 months postpartum. As explained above the CPOP moms will not be randomized, but rather their study group arm will be determined by their facilitator's randomly assigned place in the Intervention or the Control arm. Both Intervention and Control participants will receive OH tool kits at the time of the scheduled CPOP modules in the Intervention groups (CP session 3 for Maternal module and sessions 7 or 8 for Infant module).

#### *CP Women participants' and CP Facilitators' data collection.*

CP Women: At baseline and prior to the first (Maternal) of the two modules, participants will complete questionnaires, saliva sample collection, and a dental exam. These

activities will be scheduled for completion at the CP clinic site, outside of CP group scheduled time. A trained calibrated dental examiner will complete the dental exams in a private space, using portable dental equipment: chair, lamp, and stools. Study staff will administer the questionnaires and enter results directly into a tablet or laptop. The dental exam takes about 15-20 minutes and the questionnaires take about 15 minutes.

*The Maternal Intervention Module.* Intervention groups will receive the CPOP maternal intervention as part of their 3rd CP group session. Refer to Section 6.5 for details.

Approximately 10 weeks following the time of the maternal module and prior to the infant intervention module, participants complete the post-maternal module assessments consisting of a repeat dental exam and questionnaire completion. At this time, women also complete the pre-infant intervention module assessments. These consist of questionnaire assessment of infant OH knowledge and attitudes. Women receive their incentives within a week following completion of the assessments.

*The Infant Intervention Module.* The infant module is presented as part of the 7th or 8th CP session. Refer to Section 6.5 for details.

Approximately 2 weeks following the presentation of the Infant OH module, participants complete the post-infant OH module questionnaire assessment, repeating the earlier pre-module assessment. This may be done online with REDCap, email, or over the phone with an interview process. Women receive their incentives within a week following completion of the assessments. This is the final activity to occur during the prenatal period. Participants will receive a note from the study thanking them for their participation up to this point and reminding them that we will stay in touch with them about the study and will follow-up with them when their infants are about 10 months of age to schedule the 12-month postpartum visit.

When an infant is approximately 10 months of age, study staff will contact families to remind them of the final assessment to take place at infant age 12 months. We will assess eligibility of the infant to participate in the follow-up and confirm mother's intention to complete the final assessment. If the infant is ineligible to participate, the mother will still be eligible to complete the final assessment. The 12-month visit time will be scheduled.

The 12-month visit will occur at the participant's home or another location that is convenient for the mother and baby. Women will complete questionnaires and saliva collection procedures for assessment of salivary bacteria. The infants will complete a saliva collection procedure. Women receive their incentives within a week following completion of the assessments.

CP Facilitator participants: The CP facilitators will complete assessments of acceptability and feasibility of the CPOP Intervention at the time that study activities have come to a close in their clinics. This will include evaluation of their: satisfaction with the training and the amount of time taken to prepare for and implement the CPOP modules in their

groups; perceived value of CPOP to CP moms; perceived scalability of the interventions into the broader standard CP curriculum; and overall perceptions of the benefits versus burdens associated with the changes needed to accommodate CPOP modules in CP sessions. These data will help inform future implementation when CPOP is scaled up and disseminated broadly. These will be done online through REDCap.

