## PROTOCOL SUMMARY

**Title:** CenteringPregnancy Oral Health Promotion (CPOP) Clinical Trial

**Précis:** A five-year, Phase III, multi-site, cluster randomized controlled clinical trial will evaluate the efficacy of the CenteringPregnancy (CP) Oral Health Promotion (CPOP) intervention. Intervention and control groups will be drawn from 5 CP sites. Prenatal care facilitators will conduct the intervention in group prenatal care sessions. With 2-5 CP facilitators per site (14 facilitators), conducting 3-4 CP groups each (49 CP groups with 8 mother/child dyads per group), the total study population will be approximately 392 mother-child dyads. CP facilitators will be randomly assigned to either the: 1) intervention arm and deliver the CPOP intervention; or 2) control arm and deliver the usual CP curriculum. The CPOP intervention consists of two 15-minute modules: 1) maternal oral health (OH) and 2) infant OH. The data collection will continue through 12 months postpartum. For the maternal OH module, pre- and post-intervention dental exams of gingival OH and Plaque Levels, and knowledge, attitudes and behavior (KAB) questionnaires during the prenatal period will be used to assess maternal OH outcomes. For the infant OH module, pre and post-module KAB questionnaires will be completed during the prenatal period. Infant OH risk status – the presence of caries-causing bacteria (*mutans streptococci* and *Lactobacilli*) in saliva of both mother and infant will be assessed when the infant is 12 months of age to determine differences in study arms. Analyses will include generalized linear mixed model regressions testing a treatment by time interaction to determine the significance of differences between intervention arms from pre-to post- intervention on the outcome variables. Additional analyses (Secondary Aim 2) will test mediation effects of knowledge, attitudes, and behaviors on relationships between treatment arm and primary study outcomes.

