**Objectives:**

**Primary Aim 1:** Determine if women in CP groups that include the CPOP intervention as part of their CP prenatal care will have significantly greater improvement in clinical OH and hygiene outcomes during pregnancy (reduced % sites with bleeding on probing (BOP), reduced % sites with probing depths  $\geq 4$ mm (PD4), and reduced Plaque Index scores) compared to women receiving CP usual care.

**Primary Aim 2:** Determine if infants of mothers in CP groups that include the CPOP intervention as part of their CP prenatal care will be significantly less likely to have the presence of caries-causing salivary

bacteria (*mutans streptococci*) at 12 months of age, compared to infants of mothers receiving CP usual care.

**Secondary Aim 1:** Determine if women in CP groups that include the CPOP intervention as part of their CP prenatal care, compared to women receiving CP usual care will have significantly greater increases in:

- Maternal OH knowledge, attitudes, and hygiene behaviors during pregnancy;
- Maternal infant-related OH knowledge and attitudes during pregnancy and at 12 months postpartum; and
- Maternal OH practices with their infant at 12 months postpartum.

**Secondary Aim 2:** Determine if infants of mothers in the CPOP intervention groups are significantly less likely to have the presence of caries-causing salivary bacteria (*Lactobacilli*) at 12 months of age, compared to infants of mothers receiving CP usual care.

**Secondary Aim 3:** Determine if maternal OH knowledge, attitudes, and/ or behaviors mediate the relationships between intervention arm and maternal OH and infant OH risk (salivary bacteria incidence) outcomes.

**Population:** 392 healthy mother-infant dyads coming from a broad range of socio-demographic backgrounds. Women receiving their prenatal care in CenteringPregnancy® group prenatal care programs will be enrolled into the CPOP study from the 2nd through prior to the 3rd of their 10 scheduled CP sessions. CP group care is available at clinics and hospitals in the San Francisco Bay Area. CPOP participants will be involved in the study from their study enrollment during pregnancy through 12 months postpartum. Women will participate during their pregnancies within their prenatal care sessions and data collection visits to complete assessments and dental examinations. Both mothers and infants will participate at 12 months postpartum.

**Phase:** III

**Number of Sites:** 5 sites

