##### **The Maternal Intervention Module:**

This is presented in the 3rd CP session when the session topics focus on maternal needs and care. (See Section 2.2 for description of timing of CP Sessions.). The facilitator:

- 1) Introduces the topic of OH during pregnancy and distributes OH tool kits containing a toothbrush, toothpaste, and dental floss.
- 2) Leads an interactive discussion of: 1) common OH problems and asks women to share their experiences with these; 2) the importance of OH for the mother and the infant; and 3) the importance of receiving dental care during pregnancy and routinely afterwards. During this, the women are encouraged to discuss their opinions, beliefs and concerns about OH and OH care. The facilitator will build on

the women's basic knowledge and will direct and expand explanations as needed to clarify facts versus folk beliefs.

- 3) Discusses the importance of OH self-care and will lead the group in step by step tooth brushing instructions and dry brushing practice, using supplies from the tool kits. The facilitator will give feedback as needed for each woman. She will explain the rationale for learning the Eastman Interdental Assessment and will instruct and guide the women to do the assessment using toothpicks and mirrors. In subsequent CP sessions, the women will conduct the toothpick test at the beginning of their sessions which is a check in time during which they monitor and record their weights and blood pressures and receive an assessment from the prenatal care provider facilitators. Women will have attended their baseline dental exams and the presence of severe periodontal issues will have been brought to their attention with the recommendation that they seek treatment as soon as possible.
- 4) Distributes 2 illustrated pages: 1) instructions for proper tooth brushing and flossing technique; and 2) summary review of the important elements for good OH.

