### 7.3 Intermediate Visits

#### 7.3.1 Visit 2 (Day 14 ± 14) Maternal Intervention Administration

The range of +/- days is broad because the baseline data could be collected in a range of approximately 28 days between CP sessions 2 and 3, but prior to the administration of the CPOP Maternal Module in CP Session 3.

- Takes place among participants in the Intervention arm only

- Administer the maternal OH module in Intervention Arm
- Record participation and attendance at the intervention

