#### **7.3.2 Visit 3 (Day 84+/- 15): Post-Maternal & Pre-Infant Intervention Data Collection**

- Takes place prior to administration of the CPOP Infant Module occurring in Session 7 or 8
- Post-Maternal Intervention and Pre-infant Intervention questionnaire assessments
- Dental Examinations

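### Infant-related knowledge and attitudes are first measured after the maternal module, so the pre-to-post interaction estimates what the infant module adds, not the whole CPOP effect in Secondary Aim 1

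*Combined protocol and SAP*

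**What the plan says.** **Aim.** One part of Secondary Aim 1 (Protocol Summary, Objectives) is that women in CPOP groups will show greater increases than usual-care women in "Maternal infant-related OH knowledge and attitudes during pregnancy and at 12 months postpartum". Section 3.1.3 and Section 12.1 (Secondary Hypothesis 1) put the question the same way. CPOP is defined in the Protocol Summary as the maternal and infant modules together.

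**Timing.** Section 4 places the second data collection "Approximately 10 weeks following the time of the maternal module and prior to the infant intervention module". It then adds: "At this time, women also complete the pre-infant intervention module assessments". "These consist of questionnaire assessment of infant OH knowledge and attitudes". Section 7.3.1 is headed "Visit 2 (Day 14 ± 14) Maternal Intervention Administration", and Section 7.3.2 puts the "Post-Maternal Intervention and Pre-infant Intervention questionnaire assessments" at Day 84 ± 15. In Table 1 and Appendix A the baseline cell for the infant-related questionnaire is empty. Section 8.1 lists only demographics and the pre-maternal questionnaire at baseline.

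**Content of the earlier module.** Section 6.1 lists among the maternal module's discussion topics "the importance of OH for the mother and the infant". Section 3.2.2 names importance as one of the infant-related attitudes.

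**Analysis.** The Protocol Summary describes models "testing a treatment by time interaction to determine the significance of differences between intervention arms from pre-to post- intervention on the outcome variables". For secondary outcomes, Section 12.4 names multilevel linear models and gives no reference time and no deciding contrast.

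**The concern.** The questionnaire that serves as the pre-value for infant-related outcomes is completed when intervention women have already had one of the two modules. Control facilitators do not present the modules (Section 4), so any carry-over is confined to one arm. A change score or interaction that starts from this point removes whatever the maternal module has already achieved.

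At stake is how a secondary result is read. Section 2.3 reports that in the pilot mothers' ratings of infant OH importance rose more in the intervention group (p=0.003). That is the infant-related attitude with prior support, and also the one that the maternal module's content touches most directly. A weak or null interaction could be reported as CPOP failing to change it, when part of the change already lies in the reference value.

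**Working it through.** **1. Reproduce the stated interval.** Maternal module: Day 14, window 0 to 28 (Section 7.3.1). Pre-infant questionnaire: Day 84, window 69 to 99 (Section 7.3.2).

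- Nominal gap: 84 − 14 = 70 days = 10.0 weeks, which agrees with the interval given in Section 4.
- Shortest gap within the windows: 69 − 28 = 41 days.
- Longest gap: 99 − 0 = 99 days.

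Within the visit windows the pre-infant questionnaire never precedes the maternal module.

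**2. What each contrast estimates.** Let D be the total CPOP effect on an infant-related score at Mid-Study 2, and f the share already present at Mid-Study 1. The arm difference is then fD at Mid-Study 1 and D at Mid-Study 2.

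- Interaction with Mid-Study 1 as reference: D − fD = (1 − f)D.
- Arm difference at Mid-Study 2 alone: D.
- Change from a Day 0 reference: D − 0 = D.

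With D = 0.40 as an example, the interaction gives 0.40, 0.30 and 0.20 at f = 0, 0.25 and 0.50. The other two contrasts give 0.40 throughout. A simulation returned the same values to within 0.004. A contrast from Mid-Study 1 to 12 months subtracts the same fD.

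**3. Illustration of what a given f would cost.** The documents do not give f, so 0 to 0.5 is an assumed range. Section 12.2 assumes 80% power at two-tailed α = 0.05 but states no power for this outcome; 80% is borrowed here only as a starting point. With the standard error held fixed,

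power = Φ[(1 − f)(1.960 + 0.842) − 1.960].

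| f | Share of effect estimated | Power |
|---|---|---|
| 0 | 1.00 | 0.80 |
| 0.10 | 0.90 | 0.71 |
| 0.20 | 0.80 | 0.61 |
| 0.25 | 0.75 | 0.56 |
| 0.50 | 0.50 | 0.29 |

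**4. Where f is likely to be positive.**

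- *Importance.* The maternal module covers it (Section 6.1), and the pilot's maternal intervention gave a small but significant rise in ratings of OH importance (Section 2.3). A positive f is plausible.
- *Knowledge and self-efficacy.* Saliva sharing, infant feeding, cleaning the infant's mouth and the first dental visit are listed only for the infant module (Sections 2.3 and 6.1). The pilot's maternal intervention brought no significant gain in OH knowledge or self-efficacy. Here f may be close to zero.

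**The case against.** The strongest reply is that the design is deliberate. The Protocol Summary ties a pre and a post questionnaire to the infant module, and Sections 4, 7.3.2 and 8.1 all label the Mid-Study 1 questionnaire as pre-infant. As an estimate of the infant module's increment, the Mid-Study 1 to Mid-Study 2 contrast is valid. That stands. But Secondary Aim 1 is not written for the increment, and nowhere do the documents say that this contrast answers only the narrower question.

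Second, the total effect is not lost. Section 12.4 also says that arm differences at follow-up will be interpreted, and these do not subtract the maternal module's effect. This stands in part: that sentence belongs to the primary analyses, and the text on secondary outcomes does not say which contrast decides.

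Third, the overlap is narrow. Section 2.3 words the maternal module's topic as the importance of the mother's own oral health for mother and infant, which is less than Section 6.1 says. This stands, and it limits the point mainly to importance.

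A reader might also infer that 20% to 50% of the effect on all infant-related outcomes disappears, with power falling to 0.61 or 0.29. The documents do not support this. The share is assumed, zero is possible, the starting power belongs to no calculation for this outcome, and another contrast would have a different standard error.

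Nor is the wording about increases in practices with the infant a design fault. No infant exists before the 12-month visit, so an increase cannot be observed, but Section 3.2.2 already frames this outcome as a difference.

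**Conclusion.** The point holds as a mismatch between aim and contrast. The timing is certain: the first infant-related measurement falls nominally 70 days, and within the windows at least 41 days, after a module with some infant content. The interaction described in the Protocol Summary therefore estimates (1 − f) of the CPOP effect. As an answer to Secondary Aim 1 it is biased toward no effect for any positive f, assuming that the carry-over runs in the same direction as the total effect.

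The size cannot be computed from the documents. A positive f is most plausible for infant OH importance and may be near zero for knowledge and self-efficacy. Only these secondary outcomes are concerned. The maternal primary outcomes have a Day 0 baseline, and infant mutans streptococci is compared between arms at 12 months only. This is an inexpensive improvement worth making; it does not threaten the trial's main conclusions.

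**What to change.** **Analysis wording (enough by itself).** In Section 12.4, state that the CPOP effect on infant-related knowledge and attitudes is tested by the between-arm difference at Mid-Study 2 and at 12 months, without Mid-Study 1 as the reference. Label the Mid-Study 1 to Mid-Study 2 group-by-time interaction as the infant-module increment. This needs no new data. Its cost is that no pre-value of the same score is available to absorb chance imbalance between the two sets of facilitators (8 and 6).

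**If the Visit 1 questionnaire can still be changed.** Add the infant importance, knowledge and self-efficacy items there and use Visit 1 as the pre-value in both arms. Section 6.0 says that no human-subject activity was under way in October 2020, so this was feasible at that time. The cost is a few more minutes at Visit 1 and slight priming of both arms; Section 2.4.2 already accepts that research procedures alone may change behaviour in control women.

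**Editorial only.** Reword the infant-practice part of Secondary Aim 1, Section 3.1.3 and Secondary Hypothesis 1 as a between-arm difference at 12 months, in line with Section 3.2.2.

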## **5. STUDY ENROLLMENT AND WITHDRAWAL**

### **5.1 Subject Inclusion Criteria**

CP Facilitators:

- CP facilitators who conduct CP groups within the 5 designated study sites;
- ages 18 and older speak, read, and write in English;
- provide informed consent

CP Women:

- speak, read, or write in English or Spanish
- enrolled in CP prenatal group care identified as study groups
- free of any condition that requires them to take antibiotic or antibacterial medication prior to dental procedures
- provide informed consent

CP Babies:

- healthy with no acute or chronic medical conditions, especially those conditions that may have resulted in hospitalizations and subsequent exposure to pathologic microorganisms
- mothers provide informed consent for their children at baseline

Dental Exam Calibration Participants:

- ages 18 and older
- free of any condition that requires them to take antibiotic or antibacterial medication prior to dental procedures
- provide informed consent

